To estimate the change in 10-year risk during the 6 months of the study, we will consider changes in LDL cholesterol and systolic blood pressure as these are causal risk factors known to be influenced by diet (16, 17). With the SMART risk model, the effect of changes in these risk factor can be estimated by using a Hazard Ratio (HR) related to these risk factors (10). Every decrease of 1.0 mmol/L in LDL-cholesterol is shown to reduce an individual's cardiovascular risk with 20%, corresponding to an HR of 0.80 (18). Per decrease of 10 mmHg for systolic blood pressure, cardiovascular risk is estimated to be reduced with 22%, hence a HR of 0.78 is used (19). Multiplying the effects of the changes in LDL-cholesterol and systolic blood pressure with the baseline risk, gives us the predicted change in 10-year risk at the end of the intervention.

In short, 10-year CVD risk at six months is calculated as  $10\text{-year CVD risk at baseline} * (0.78^{\text{LDL-c end} - \text{LDL-c baseline}}) * (0.8^{(\text{SBP end} - \text{SBP baseline})/10})$ . By subtracting the 10-year CVD risk at six months from the 10-year CVD risk at baseline, the change in SMART risk score will be calculated.

*Table 1 Example calculation of 10-year CVD risk at six months using changes in LDL-cholesterol and systolic blood pressure*

Baseline risk	Change in LDL-c	Change in SBP	6 months risk	Change in risk
1%	increased with 1mmol/l	increased with 3 mmHg	$1 * (0.78^{-1}) * (0.8^{3/10}) = 1.2\%$	+0.2%
20%	decreased with 1mmol/l	decreased with 5 mmHg	$20 * (0.78^1) * (0.8^{5/10}) = 13.9\%$	-6.1%
20%	decreased with 0.5 mmol/l	decreased with 2 mmHg	$20 * (0.78^{0.5}) * (0.8^{2/10}) = 17.3\%$	-2.7%
80%	no change	increased with 1 mmHg	$80 * (0.78^0) * (0.8^{1/10}) = 80.9\%$	+0.9%

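### The formula for 6-month risk, the primary outcome, reverses the exponents and swaps the two hazard ratios, so a fall in LDL-cholesterol or blood pressure is scored as a rise in risk

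*SAP*

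**What the plan says.** SAP section 2.7 (Primary endpoints) defines the 6-month risk in three places.

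- **Text.** For each 1.0 mmol/L decrease in LDL-cholesterol the risk falls by 20%, "corresponding to an HR of 0.80". For each 10 mmHg decrease in systolic blood pressure (SBP), "cardiovascular risk is estimated to be reduced with 22%, hence a HR of 0.78 is used".
- **Formula.** After "In short, 10-year CVD risk at six months is calculated as", the baseline risk is multiplied by 0.78 raised to (LDL end − LDL baseline) and by 0.8 raised to (SBP end − SBP baseline)/10.
- **Table 1.** Four worked examples. The row for a 20% patient whose LDL falls by 1 mmol/L and SBP by 5 mmHg is printed as "20 * (0.78^1) * (0.8^{5/10}) = 13.9". The row for an 80% patient whose SBP rises by 1 mmHg is printed as "80 * (0.78^0) * (0.8^{1/10}) = 80.9".

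The change score is obtained "By subtracting the 10-year CVD risk at six months from the 10-year CVD risk at baseline", which makes an improvement positive. Table 1 shows improvements as negative (for example −6.1%).

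Section 4.5 makes the 6-month score the dependent variable of the primary ANCOVA, adjusted for baseline score and hospital.

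**The concern.** Both hazard ratios are below 1 and are defined per decrease. They must therefore be raised to the size of the decrease, baseline minus end. The formula uses end minus baseline, so a fall gives a negative exponent and a factor above 1. The formula also exchanges the two constants given in the paragraph before it, and Table 1 repeats that exchange in every row.

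The formula generates every 6-month value of the primary outcome. Coded literally, it reverses the sign of the treatment contrast. Correcting only the sign leaves the LDL and SBP weights exchanged. A programmer who turns to Table 1 finds no single rule to code: the stated result in row 1 rests on an expression that scores an SBP rise as lowering risk, while the stated result in row 4 scores an SBP rise as raising it. The SAP does not say whether text, formula or table governs.

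**Working it through.** **Inputs (all from SAP section 2.7).** HR 0.80 per 1 mmol/L LDL decrease; HR 0.78 per 10 mmHg SBP decrease; the four Table 1 patients. Write ΔLDL and ΔSBP for end minus baseline.

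**Rules evaluated**

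- (a) Formula as printed: baseline × 0.78^ΔLDL × 0.8^(ΔSBP/10)
- (b) The expression printed in each Table 1 row
- (c) Signs reversed, constants still swapped: baseline × 0.78^(−ΔLDL) × 0.8^(−ΔSBP/10)
- (d) Constants as in the text, signs reversed: baseline × 0.80^(−ΔLDL) × 0.78^(−ΔSBP/10)

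| Row | Baseline | ΔLDL | ΔSBP | Stated | (a) | (b) | (c) | (d) |
|---|---|---|---|---|---|---|---|---|
| 1 | 1% | +1 | +3 | 1.2 | 0.73 | 1.20 | 1.37 | 1.35 |
| 2 | 20% | −1 | −5 | 13.9 | 28.7 | 13.95 | 13.95 | 14.13 |
| 3 | 20% | −0.5 | −2 | 17.3 | 23.7 | 16.9 | 16.9 | 17.02 |
| 4 | 80% | 0 | +1 | 80.9 | 78.2 | 78.2 | 81.8 | 82.01 |

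**Row 2 in full**

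- (a) 20 × 0.78^(−1) × 0.8^(−0.5) = 20 × 1.282 × 1.118 = 28.7
- (c) 20 × 0.78 × 0.8^0.5 = 20 × 0.78 × 0.894 = 13.95
- (d) 20 × 0.80 × 0.78^0.5 = 20 × 0.80 × 0.883 = 14.13

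**Reading the table**

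1. Column (a) reproduces none of the stated results, and in every row it moves risk in the opposite direction to the stated result.
2. Column (b) reproduces row 1, and row 2 if truncated. The expressions in rows 3 and 4 give 16.9 and 78.2, not 17.3 and 80.9.
3. Row 1 matches only because its expression has exponent −1 for an LDL increase and +3/10 for an SBP increase. With consistent signs it would be 1.37 (c) or 1.35 (d).
4. None of the rules tried gives all four stated results. One further variant, (c) with SBP counted per 20 mmHg, gives 17.27 and 80.90 in rows 3 and 4 but 1.33 and 14.75 in rows 1 and 2.

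**Size of the swap alone.** In row 2 it is 13.95 against 14.13. For an LDL fall of 1 mmol/L alone, the swap scores a 22% reduction in place of 20% (22/20 = 1.10). For an SBP fall of 10 mmHg alone, it scores 20% in place of 22% (20/22 = 0.91). When both falls occur together the product is the same, 0.78 × 0.80 = 0.624.

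**Trial-level illustration.** The inputs are assumptions, not SAP figures: median baseline risk 17%, true effects of −0.2 mmol/L LDL and −4 mmHg SBP, SDs of change 0.5 and 13, 57 patients per arm. The ANCOVA contrast is −2.6 percentage points with the correct formula, +2.9 with the printed one, and −2.5 with the swap as the only error. The contrast also reversed in all 12 scenarios tried with baseline risk from 10% to 25% and varied LDL and SBP effects.

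**Scale (secondary).** Figure 1 has survival form, 1 − 0.81066^exp(·), in which a hazard ratio acts on the exponent: 6-month risk = 1 − (1 − baseline)^HR. With the constants and signs of (d), this gives 1.34, 14.59, 17.30 and 80.79 for the four rows. For row 2 the reduction is 20 − 14.59 = 5.41 points, against 20 − 14.13 = 5.87 by direct multiplication, an overstatement of about 8% (5.87/5.41). For the reductions examined, the overstatement is about 8–11% at 20% baseline risk and 21–27% at 40%.

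**The case against.** The intended direction is not in doubt: the prose says decreases reduce risk, and rows 2 and 3 of Table 1 score them that way. LDL and SBP are reported next to the risk score, so an analyst would probably notice both falling while risk rises. That is fair, and it makes the reversal a hazard of literal coding and not a certain outcome. It does not make the definition usable, and the group labels stay masked until the primary outcome has been analysed (section 2.4), which removes one natural check on the contrast.

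The positive SBP exponents in rows 1 and 4 might be minus signs lost when the PDF was read. Restoring them gives 1.37 and 81.8, still not 1.2 and 80.9, and explains neither row 3 nor the formula.

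Three further points stand in part:

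- The swap is minor, and its effect on the contrast depends on the mix of LDL and SBP change. The roughly 4% shift in the illustration is specific to that scenario.
- The direction of subtraction for change does not enter the primary test, which models the 6-month score. It affects only the reported change.
- Multiplying a hazard ratio onto a risk is a method the SAP states openly, so the hazard scale is an improvement and not the correction of a contradiction. Risks above 100% are remote: with LDL up 1 mmol/L and SBP up 10 mmHg, rule (d) exceeds 100% only for baseline risks above 62.4% (100 × 0.80 × 0.78).

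**Conclusion.** The concern holds and must be fixed before the primary analysis. Text, formula and worked examples contradict one another on the variable that the primary ANCOVA analyses. The reversed exponent carries the weight: the row 2 patient scores 28.7% where the stated hazard ratios give 14.1%, and all four examples go the wrong way. The swapped constants are a definite but small error (13.95 against 14.13 in that row). Table 1 cannot settle the matter, because two of its rows fail their own arithmetic and no rule tried reproduces all four. These results use only figures in the SAP. The trial-level contrast, −2.6 turning into +2.9, rests on the assumed inputs; its reversal held across the range of scenarios tried.

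**What to change.** 1. Replace the formula in section 2.7 with: risk at 6 months = baseline risk × HR, where HR = 0.80^(LDL baseline − LDL end) × 0.78^((SBP baseline − SBP end)/10).
2. Define change as 6 months minus baseline, so that a negative value means improvement, in the text as in Table 1.
3. Recompute all four rows of Table 1 from the final code. Under step 1 they become 1.35% (+0.3), 14.1% (−5.9), 17.0% (−3.0) and 82.0% (+2.0). Keep them as a test of the analysis program.
4. Optional: apply the same HR on the hazard scale, 1 − (1 − baseline risk)^HR, which agrees with the form of Figure 1 and keeps risk below 100%. If this is adopted, say so in the SAP and recompute Table 1 accordingly.

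The cost is SAP wording and a few lines of code before the groups are unblinded. No new data are needed.

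### Two of the four worked examples of the primary outcome (SAP section 2.7) print six-month risks that do not follow from the stated scaling of blood pressure per 10 mmHg

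*SAP*

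**What the plan says.** SAP section 2.7 gives the SBP effect in words as "Per decrease of 10 mmHg for systolic blood pressure, cardiovascular risk is estimated to be reduced with 22%, hence a HR of 0.78 is used". The six-month risk formula below it contains the term "0.8^{(\text{SBP end} - \text{SBP baseline})/10", so it also scales SBP per 10 mmHg. The example table that follows prints four expressions, each dividing the SBP change by 10:

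- Example 1 (baseline 1%, LDL-c up 1 mmol/L, SBP up 3 mmHg): "1 * (0.78^{-1}) * (0.8^{3/10}) = 1.2" percent, change +0.2.
- Example 2 (baseline 20%, LDL-c down 1, SBP down 5): "20 * (0.78^1) * (0.8^{5/10}) = 13.9" percent, change -6.1.
- Example 3 (baseline 20%, LDL-c down 0.5, SBP down 2): "20 * (0.78^{0.5}) * (0.8^{2/10}) = 17.3" percent, change -2.7.
- Example 4 (baseline 80%, LDL-c unchanged, SBP up 1): "80 * (0.78^0) * (0.8^{1/10}) = 80.9" percent, change +0.9.

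Under section 4.5, the six-month risk obtained in this way is the dependent variable of the primary ANCOVA.

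**The concern.** In examples 3 and 4 the number after the equals sign is not the value of the expression before it. The gaps are too large for rounding, and the change column repeats the same values, so neither is a slip in a single cell.

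Six-month risk differs from baseline risk only through LDL-c and SBP, and these four lines are the only numerical check that the SAP gives on the derivation. A programmer who codes the formula and tests it against the table will fail examples 3 and 4. A programmer who adjusts the code until those two agree could arrive at a different SBP scaling from the one stated. If the numbers came from a spreadsheet or function that is also used for scoring, the weight given to SBP in the primary outcome would differ from what the SAP describes.

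**Working it through.** **Inputs.** All come from SAP section 2.7: the baseline risks, LDL-c changes, SBP changes and printed results listed above, and the factors as the table uses them (0.78 for LDL-c, 0.8 for SBP).

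**Step 1: evaluate each expression exactly as printed**, baseline × 0.78^a × 0.8^b.

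| Example | Expression | Value | Printed | Agrees? |
|---|---|---|---|---|
| 1 | 1 × 0.78^(-1) × 0.8^0.3 | 1.199 | 1.2 | yes |
| 2 | 20 × 0.78^1 × 0.8^0.5 | 13.953 | 13.9 | only by truncation (rounds to 14.0) |
| 3 | 20 × 0.78^0.5 × 0.8^0.2 | 16.893 | 17.3 | no |
| 4 | 80 × 0.78^0 × 0.8^0.1 | 78.235 | 80.9 | no |

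Example 4 as printed lowers the risk although SBP rises. With the sign reversed, 80 × 0.8^(-0.1) = 81.805, which still differs from 80.9. The changes should be 16.9 - 20 = -3.1 for example 3 and, with the sign reversed, 81.8 - 80 = +1.8 for example 4.

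**Step 2: find the divisor that would give the printed results**, allowing for rounding to one decimal.

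- Example 3: 20 × 0.78^0.5 = 17.664. Solving 17.664 × 0.8^(2/d) for results from 17.25 to 17.35 gives d from 18.8 to 24.9.
- Example 4, sign reversed: solving 80 × 0.8^(-1/d) for results from 80.85 to 80.95 gives d from 18.9 to 21.1.
- Example 2, allowing truncation (13.85 to 14.0): d from about 9.4 to 10.3.

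**Step 3: put d = 20 into every example**, with the signs as printed except in example 4.

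- Example 3: 20 × 0.78^0.5 × 0.8^(2/20) = 17.27, which matches.
- Example 4, sign reversed: 80 × 0.8^(-1/20) = 80.90, which matches. Without the reversal it is 79.11, which does not.
- Example 2: 20 × 0.78 × 0.8^(5/20) = 14.75, which does not match.
- Example 1: 1.24 against 1.20 with d = 10. Both print as 1.2, so this example cannot tell the divisors apart.

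**Step 4: try other explanations.** I varied the divisor (10 or 20), the hazard ratios (as in the table, or exchanged as in the text), the sign, and the scale (multiplying the risk, or 1 - (1 - risk)^HR). Among these, only a divisor of 20 with the table's factors, multiplying the risk and letting it rise with SBP, gives both 17.3 and 80.9. Example 3 alone also comes out at 17.30 with the text's hazard ratios on the hazard scale and a divisor of 10, but that gives 80.79 for example 4 and 14.59 for example 2.

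**Step 5: size, if 20 had been used.** A factor of 0.8 per 20 mmHg is 0.8^0.5 = 0.894 per 10 mmHg, which is half the effect on the log scale. For a 5 mmHg fall at 20% baseline risk, the SBP contribution would be 20 × (1 - 0.8^0.25) = 1.1 points, where a divisor of 10 gives 20 × (1 - 0.8^0.5) = 2.1 points.

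**The case against.** The strongest reply is that a divisor of 20 appears nowhere in the SAP. The text, the formula and all four expressions say 10. A divisor of 20 also cannot be told apart from a divisor of 10 applied to half the listed SBP change: 20 × 0.78^0.5 × 0.8^(1/10) is again 17.27, and 80 × 0.8^(-0.5/10) is again 80.90. Results left over from different example inputs would therefore explain both lines with no scaling error. The four lines do not look like output from one function either: example 1 uses opposite signs for two increases, example 2 excludes 20, and example 4's printed sign contradicts its own result. All of this stands.

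A reader might infer that the primary analysis halves the blood pressure effect and is biased towards no difference. The document does not support that. The scoring code is not shown, the written rule divides by 10, and a smaller SBP weight would also reduce SBP-driven variation in both arms, so its effect on the test has not been shown. Nor should a single patient's shift of about one point be set against the 3.3% between-group difference in section 2.9, which is a different quantity.

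It can also be said that the same section has larger faults. The text assigns the hazard ratios the other way round from the formula (for LDL-c it says "reduce an individual's cardiovascular risk with 20%, corresponding to an HR of 0.80"), and the formula's exponent, end minus baseline, makes a fall raise the risk. Repairing these means recomputing the table anyway. That is true, but it does not make this point redundant. With the text's hazard ratios, risk rising with each factor, and a divisor of 10, examples 3 and 4 become 17.0 and 82.0, still not the printed values, so the divisor needs its own check.

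**Conclusion.** Examples 3 and 4 are wrong as written. Their printed results miss the stated calculation by 0.4 points (17.3 against 16.9) and by 0.9 points (80.9 against 81.8 with risk rising with SBP; the gap is 2.7 points against the literal 78.2). This part is plain arithmetic and rests on no assumption beyond the table's own factors.

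The cause is not known. Halved SBP scaling accounts for both lines and is worth ruling out, but it remains an inference from two numbers. Example 2 points to 10, and example 1 is uninformative. The figures of 0.894 per 10 mmHg, and of 1.1 against 2.1 points, describe what would follow if the scoring code shared that divisor and used the table's factor of 0.8. They do not describe the planned analysis. The point deserves correction because the error sits in the operational definition of the primary outcome and in its only worked check.

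**What to change.** Confirm that the scoring code divides the SBP change by 10, as the formula states. In the same revision, reconcile which hazard ratio belongs to LDL-c and which to SBP, and settle the sign of the exponents so that text, formula and examples agree. Then regenerate all four examples by running that code, print risk and change to one decimal with consistent rounding, and keep the four input-output pairs as a test that must pass before the code is run on trial data. The cost is a few minutes of checking and one corrected table. Nothing in the design, data collection or analysis model changes.

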## 2.8 Secondary endpoints

As secondary outcomes, changes in LDL-cholesterol, body weight, CRP and systolic blood pressure will be presented and compared between groups. Similarly, the change in proportion of individuals using lipid lowering agents, antiplatelet or anticoagulant agents, or blood pressure lowering agents will be presented and compared between groups.

Changes in diet quality, as assessed with the Dutch Healthy Diet index, will be presented for the total population and for the two groups separately but will not be compared with statistical tests. Changes in smoking habits will be presented for the total population and for the two groups separately as % of individuals smoking at baseline and at 6 months.

## 2.9 Sample size calculation

The study was powered to detect a difference in estimated 10-year CVD risk between the intervention and control group at 6 months of 3.3% (20), with an assumed standard deviation of 6.3% (21). Based on those numbers, a sample size of 114 patients (57 patients per group) was needed to provide a

power of 80% with an alpha 0.05. Considering a possible 20% dropouts, the required sample was increased to 144 patients.

### 3. Population and variables

#### 3.1 Analysis population

The patient populations to be studied are defined as follows:

##### 3.1.1 Intention-to-treat

The intention-to-treat (ITT) population includes all subjects who were assigned a randomization number. The ITT population is considered the main analysis population. Missing data necessary for the calculation of the primary outcome will be imputed (see 4.4 Missing data for an explanation of procedures).

##### 3.1.2 Per protocol

The following per protocol (PP) populations have been defined:

- PP-Comp: This population includes all subjects in the ITT population who visited the dietitian 5 times or more in the intervention group.
- PP-Diet: This population includes all subjects in the ITT population who improved  $\geq 1$  SD on Eetscore compared to baseline in the intervention group, and excludes all subjects who improved  $\geq 1$  SD on Eetscore compared to baseline in the control group.

### 3.2 Subject demographics and pre-treatment characteristics

Subject demographics and pre-treatment characteristics will be summarized for the ITT and PP populations and presented per treatment group and for all subjects.

#### 3.2.1 Demographics

The summary of demographics will include gender, age at randomization, origin of parents and educational level. Educational level will be shown in categories as defined by the Centraal Bureau voor Statistiek (CBS).

#### 3.2.2 Medical history and risk factors

The summary of medical history (type of CVD and time since last event) and CVD risk factors will include body weight, body mass index, waist circumference, total cholesterol (mmol/L), high-density lipoprotein cholesterol (mmol/L), low-density lipoprotein cholesterol (mmol/L), triglycerides (mmol/L), C-reactive protein (mg/L), diastolic blood pressure (mmHg), systolic blood pressure (mmHg), time since last event (y), type of CVD, smoking, alcohol use, level of physical activity.

Smoking status will be shown as percentage of people being current, former, and never smokers. Level of physical activity will be presented as minutes per week moderate to vigorous physical activity (MVPA). Alcohol use will be presented as alcohol consumptions per week. Type of CVD will be shown in categories (n, %) as used in the SMART-risk predictor tool:

- Coronary Artery Disease
- Cerebrovascular Disease
- Aortic Aneurysm
- Peripheral Artery Disease
- Other

### 3.2.3 Medication

The summary of medication use will be shown as proportion (n, %) of patients taking lipid lowering agents (C10), antiplatelet or anticoagulant agents (B01) or blood pressure lowering agents (C02 + C03 + C07 + C08 + C09).

## 4. Statistical analysis

### 4.1 Significance

All statistical tests will use a significance level of  $\alpha=0.05$ . Two-tailed tests will be performed for all analyses involving statistical testing. Confidence intervals will be presented with a 95% degree of confidence.

### 4.2 Multiplicity

No adjustment for multiplicity is planned within any of the analysis performed.

### 4.3 Data summarization

Summary statistics will consist of the number and percentage of responses in each category for discrete variables, and the mean  $\pm$  standard deviation (SD), or the median and interquartile range for continuous variables. All percentages will be rounded to one decimal place. All analysis and summary tables will show the population sample sizes in the column headings.

### 4.4 Missing data

Researchers were instructed to obtain complete CRFs, but participants dropping out of the study resulted in missing data. Data is assumed to be missing at random (MAR). Missing data necessary for the calculation of the primary outcome will be imputed by chained equations with the MICE package for R software ( $m=10$  imputations, iterations =10) (22). In more detail, with this method missing values are imputed by using a model that incorporates random variation. Every variable (except for personID) in the dataset is considered a potential predictor for imputing missing values in other variables.

For the imputation, ten datasets will be created and the data analysis will be performed on these ten datasets. After performing the data-analysis on the ten datasets containing the imputed data, the ten coefficients are estimated by the imputed dataset into one final regression coefficient. The variance will be estimated using the pool() function. To obtain the final coefficients we take the mean of the ten values. We calculate the variance of the estimated coefficient by factoring in the within (accounting

for differences in predicted values from the dataset regarding each observation) and between (accounting for differences between ten datasets) imputation variance. If convergence is not achieved after 10 iterations, more iterations will be used to improve convergence.

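### Ten imputations without a recorded seed leave avoidable Monte Carlo noise in the primary estimate and p-value; the test stays valid, and about 100 imputations remove most of the noise

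*SAP*

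**What the plan says.** The imputed intention-to-treat analysis is the main analysis (SAP 3.1.1). Section 4.4 assumes data missing at random and uses chained equations with 10 imputations and 10 iterations: "For the imputation, ten datasets will be created and the data analysis will be performed on these ten datasets". On the imputation model it says "Every variable (except for personID) in the dataset is considered a potential predictor for imputing missing values in other variables". On pooling it says "The variance will be estimated using the pool() function", with within- and between-imputation variance combined.

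If convergence fails, the number of iterations may be raised; there is no such provision for the number of imputations. No seed appears in 4.4, in 4.6 (Software) or elsewhere in the SAP.

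The test is at 0.05, and 4.1 states "Two-tailed tests will be performed for all analyses involving statistical testing". The only figure for missingness is the planning allowance in 2.9: "Considering a possible 20% dropouts".

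**The concern.** Multiple imputation adds a random element of its own. Two analysts with the same data, model and plan, but different seeds, get different pooled estimates and p-values. With few imputations the gap can be large enough to matter for a verdict that turns on 0.05.

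Without a recorded seed nobody else can reproduce the reported figure exactly. Section 4.4 also foresees a re-run with more iterations if convergence fails, without a criterion for convergence. Such a re-run draws new imputations and can move the p-value. At stake is the reproducibility of a borderline primary result, not the validity of the method.

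**Working it through.** **Inputs from the SAP.** 10 imputations (4.4); two-sided 0.05 (4.1); 20% dropout allowance and planned N = 144 (2.9); N = 124 in the baseline table shell (section 5); ANCOVA on 6-month risk with baseline risk and hospital (4.5).

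**Assumption.** The fraction of missing information (FMI) is not in the SAP. I take 0.20 as the main case, because simulation with 20% of 6-month outcomes missing, and imputation from arm, hospital and baseline values, gave 0.20–0.21. The range shown is 0.05 to 0.30.

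**The plan's own figure.** The 20% enters through the sample size: n per arm = 2 × (1.960 + 0.842)² × (6.3/3.3)² = 57.2, against 57 stated. Then 57/0.8 = 71.25, rounded up to 72 per arm, or 144. This reproduces, and it shows that the 20% is an allowance made in advance, not an observed rate.

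**Noise in the pooled estimate.** Hold the observed data fixed. With between-imputation variance B, the pooled coefficient varies across seeds with variance B/m. Since FMI ≈ B/T, where T is the total variance, the noise in units of the standard error is √(FMI/m):

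- FMI 0.20, m = 10: √(0.20/10) = 0.14
- FMI 0.20, m = 50: √(0.20/50) = 0.063
- FMI 0.20, m = 100: √(0.20/100) = 0.045
- FMI 0.05 and 0.10, m = 10: 0.07 and 0.10

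**Noise in the p-value.** I drew the pooled estimate with variance B/m, and the estimated B as B·χ²(m−1)/(m−1), and applied Rubin's rules with Barnard–Rubin degrees of freedom at N = 124. For a p-value of 0.05 with very many imputations:

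| FMI | SD of p, m = 10 | 95% range, m = 10 | SD of p, m = 100 | 95% range, m = 100 |
|---|---|---|---|---|
| 0.05 | 0.009 | 0.036–0.070 | 0.003 | 0.045–0.056 |
| 0.10 | 0.013 | 0.031–0.083 | 0.004 | 0.043–0.058 |
| 0.20 | 0.022 | 0.023–0.107 | 0.006 | 0.040–0.063 |
| 0.30 | 0.030 | 0.018–0.132 | 0.008 | 0.037–0.068 |

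N = 144 gives almost the same values. A full simulation with imputation, ANCOVA and pooling at 20% missing gave the same SDs as the 0.20 row.

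**Effect on the verdict, FMI 0.20.** If the many-imputation p is 0.04, 35% of seeds give p ≥ 0.05 with m = 10, and 4% with m = 100. If it is 0.06, 27% give p < 0.05 with m = 10, and 6% with m = 100. Across simulated datasets with p between 0.03 and 0.07, about 30% of seeds fell on the minority side of 0.05 with m = 10, and 10–14% with m = 100.

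**How often this arises.** With no true effect, the many-imputation p falls between 0.03 and 0.07 about 4% of the time; at 80% power, about 10%. Over all results at FMI 0.20 and m = 10, the chance that the verdict differs from the many-imputation one is about 1.4% with no effect, 4% at 80% power and 6% at power near 50%. At FMI 0.10 these are about 1%, 3% and 4%.

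**The case against.** The strongest reply is that nothing here is an error. The pooled variance already contains the between-imputation term for a finite number of imputations, so the test with m = 10 is valid and the estimate unbiased. Long-run power hardly moves: about 78% against 79% at FMI 0.20. This stands, and it limits the point to precision and reproducibility.

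A reader might infer that about a third of possible seeds would overturn the trial's conclusion. The figures do not support this. That share holds only for results already near 0.05.

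A reader might also infer that 20% of outcomes are missing. The SAP does not say so. Its imputation model admits every variable except the identifier, and section 2.5 records visits at 3 and 12 months. Where such values exist for a participant without a 6-month value, the FMI could be nearer 0.05–0.10. This may not help much: dropouts may lack later visits, and 2.5 restricts the primary analysis to the 6-month measurements, so the use of other visits in the imputation is not certain.

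Two safeguards are partial. Section 2.4 has the groups recoded until the primary outcome is analysed, which hinders choosing a seed that favours the intervention. But a two-sided p-value is the same whichever label each arm carries, so the recoding does not hide which run crosses 0.05. Section 5 plans complete-case tables, which need no seed, but these do not settle the imputed primary p-value.

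**Conclusion.** The point holds as a minor, practically free improvement. With 10 imputations the primary estimate carries Monte Carlo noise of about 0.14 standard errors if the FMI is about 0.20, and 0.07–0.10 if it is 0.05–0.10. Raising the number to 100 divides this by √10, about 3.2.

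The sizes rest on an assumed FMI, since the SAP gives no observed missing rate. They concern results near 0.05 only. If the many-imputation p is almost exactly 0.05, no number of imputations settles the verdict, so the change removes most of the noise but not all of it. Nothing in the SAP suggests that seeds have been or would be chosen for their result; it simply does not rule this out.

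**What to change.** In SAP 4.4:

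- Set 100 imputations in place of 10.
- Fix and record the seed before the primary analysis is run, and keep it for any re-run with more iterations. The seed makes the result reproducible; it does not reduce the noise.
- Report the Monte Carlo error of the treatment coefficient, √(B/m), and raise the number of imputations if it exceeds 5% of the standard error.

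The 5% limit needs m ≥ FMI/0.05²: 80 at FMI 0.20, 100 at 0.25 and 120 at 0.30. Fifty would miss it at 0.20 (6.3%). So 100 is a sensible default, with the limit covering a higher FMI.

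The cost is computing time on a dataset of 124 to 144 participants, one changed number and two added sentences.
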